## **9. Statistical Analysis Plan**

### **A. Sample size and power estimates:**

The primary outcome will be time to concordant *S. aureus*-colonization. Time to concordant *S. aureus* colonization will be expressed using an indicator variable for concordant colonization and time to concordant colonization. The a priori assumed

control group concordant colonization rate is 10% and power calculations are based on the unadjusted Cox proportional hazards model where the primary covariate is the treatment group indicator. In time to event analyses, power is driven by the number of events; i.e. number of concordant colonizations. Given our assumed control group concordant colonization rate of 10%, 38 events are required to detect a 60 percent reduction in the hazard of concordant colonization (Hazard Ratio: HR 0.4) in the intervention group with 80% power and Type I error rate of 5%. The 38 events includes a roughly 2% inflation for pre-planned interim analyses (see Section 9.B). Given that we expect 5% of the parent-neonate pairs will be non-singleton births, we increased the number of required events to 40 to account for the possible clustering of concordant colonization among non-singleton neonates. Some neonates may test positive at baseline for *S. aureus* after randomization and will not be eligible for the analysis of the primary outcome. Similarly, if one neonate from a multiple gestation birth is positive for *S. aureus* at baseline and another neonate is not, then the negative infant will be eligible. Eligible parent-neonate pairs will be assigned to either treatment or control as a unit until 40 events are confirmed. Prior to the start of the study, given our *a priori* assumption of a 10% concordant colonization rate in the control group and a HR of 0.40, we anticipated recruiting 400 parent-neonate pairs to achieve the required 40 concordant colonizations. With 400 parent-neonate pairs, we have roughly 80% power to detect an absolute risk difference of at least 7% for the secondary analysis of the indicator of concordant colonization within 90 days after randomization.

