### **4. Study Procedures**

#### **A. Summary**

The TREAT PARENTS Trial, or Treating Parents to Reduce Neonatal Transmission of *S. aureus*, is a placebo-controlled, double-masked, randomized clinical trial to test the hypothesis that treatment of *S. aureus* colonized parents with intranasal

mupirocin and topical chlorhexidine gluconate antisepsis will decrease neonatal *S. aureus* acquisition. All neonates admitted to the Johns Hopkins Hospital NICU and the Johns Hopkins Bayview Medical Center NICU will be pre-screened and parents will be approached for enrollment in the study. After consent and baseline screening, approximately 400 neonate-parent pairs will be randomized. Parents will receive a 5 day treatment with intranasal mupirocin plus topical chlorhexidine gluconate antisepsis or placebo.

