## **7. Study initiation and baseline data collection**

After results of the pre-randomization screening are completed, a member of the research team will contact the subject(s) to review the results and randomize the positive family units into either treatment or placebo group. After reviewing consent and the study with the parent(s), treatment will commence immediately upon assignment to treatment arm. At that time, the research team will perform the necessary baseline swabs to be sent for culture from the neonate. Neonates' screening cultures will be performed by obtaining a swab from the following anatomical sites: bilateral anterior nares, umbilicus, groin, and peri-anal area. Study team members will also gather residual samples from the clinical laboratory collected during routine clinical care. Parents will be asked about some demographic and medical history information for the researcher to complete on the case report form. Additional information will be obtained from the neonate's medical record (e.g. birth history, maternal prenatal labs).

Those neonates that test positive for *S. aureus* colonization at time of randomization will not be eligible for the primary outcome analysis and they will not contribute to the sample size required to power the primary outcome. Participants will be informed that their child is colonized with *S. aureus*, but participants will be asked to continue the assigned treatment, so secondary outcome data can be collected.

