## B. Interim Analyses

Several interim analyses will be performed. We will perform interim analyses for efficacy based on the number of accumulated primary outcomes. Specifically, we will perform an interim analysis after 20 and 30 neonates have been identified to have the primary outcome of concordant colonization. After accruing 20 neonates with the primary outcome, the standard Cox proportional hazards model with main effect of treatment will be fit to estimate the treatment effect, i.e. the hazard ratio comparing the hazard of concordant colonization comparing the intervention and control groups, and the test statistic for the treatment effect will be computed using the methods described in Section

9.C. The DSMB will review the results of the Cox proportional hazards model to determine if the trial will stop for efficacy. The **minimum** criteria for stopping for efficacy will be if the test statistic for the hazard ratio is less than  $Z_r = -2.74$ . If the trial continues, after accruing 30 neonates with the primary outcome, the Cox proportional hazards model will be fitted. The DSMB will review the results of these statistical analyses to determine if the trial will stop for efficacy. The **minimum** criteria for stopping for efficacy will be if the test statistic for the hazard ratio is less than  $Z_r = -2.36$ . If the trial continues, after accruing the 40 neonates with the primary outcome, the treatment effect will be deemed statistically significant if the test statistic for the primary analysis as described below falls within the rejection region defined by  $Z_r = -2.03$ .

To define the above rejection regions, we applied an approximation to the error spending function of O'Brien and Fleming ( $f(t) = \min\{at^3, \alpha\}$ ) such that we spend the overall Type I error rate of 0.05 as 0.0062, 0.0148 and 0.029 after accruing 20, 30 and 40 patients, respectively. The derived rejection regions at each interim analysis (i.e.  $Z_r$ ) are based on the hazard ratio (equivalent to the log-rank test comparing the survival experience in the treatment groups) using an approximation to the information available at each interim analysis (i.e. number of accumulated events at the interim analysis divided by 4).

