Planned analysis of secondary outcomes will include the following: a) Repeat the primary analysis where time to concordant colonization will not be censored at 90 days after randomization; time will be defined as the time from randomization to the first of concordant colonization or last available culture (clinical, surveillance or NICU discharge), b) Define the treatment effect as the difference in the proportion of neonates acquiring concordant *S. aureus* by 4 and 8 weeks after randomization comparing the Treatment to Control group; this treatment effect will be estimated by taking the difference in the observed proportions comparing the Treatment and Control groups with standard error estimates and confidence intervals derived from the bootstrap procedure described above, c) Using the methods described above, estimate the treatment effect on the acquisition of *S. aureus* (regardless of concordant status), treated as both time to acquisition and the binary indicator for any acquisition by 4 and 8 weeks, and d) Using the methods described above, estimate the treatment effect on neonatal *S. aureus* infection, treated as both time to infection and the binary indicator for infection by 4 and 8 weeks. For the analysis of the *S. aureus* infection, we will first consider only *S. aureus* infections that occur prior to a neonate being identified as acquiring *S. aureus* colonization. For example, if a neonate acquires *S. aureus* colonization and then has a subsequent infection 7 days later, this infection will not be included. Only clinical cultures that occur before or on the same day as the first positive surveillance culture will be

considered. The NICU has a policy to decolonize all *S. aureus* colonized neonates which will impact the risk of infection in those that are first identified as colonized. Despite the possible independent impact of neonate decolonization on *S. aureus* infection risk, we recognize the importance of reporting all *S. aureus* infections in study patients; therefore, we will repeat the analysis, including *S. aureus* infections that occur at any time during a neonate's admission in the NICU. Lastly, a descriptive analysis of neonate mortality and bloodstream infections will be conducted, estimating the rate of occurrence separately for each treatment group.

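### Section 9.A expects 40 events from 400 pairs, but its own 10% control rate and hazard ratio of 0.40 give about 28 to 30; 40 events need about 540 to 570 pairs before baseline exclusions

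*Combined protocol and SAP*

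**What the plan says.** Section 9.A states the design inputs: the assumed "control group concordant colonization rate is 10% and power calculations are based on" the unadjusted Cox model, with a hazard ratio of 0.40, 80% power and a 5% type I error rate. It requires 38 events, including about 2% for the interim looks, and raises this to 40 because 5% of pairs are expected to be multiple births. It then converts events to enrolment: "we anticipated recruiting 400 parent-neonate pairs to achieve the required 40 concordant colonizations".

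The same section makes enrolment event-driven: "Eligible parent-neonate pairs will be assigned to either treatment or control as a unit until 40 events are confirmed". The design summary in section 4.A does not repeat that rule and says only that "approximately 400 neonate-parent pairs will be randomized". Section 9.B ties the looks to event counts: "we will perform an interim analysis after 20 and 30 neonates have been identified to have the primary outcome of concordant colonization", with the final analysis at 40.

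Section 4.C.7 adds that neonates found positive at baseline are left out of the primary analysis and that "they will not contribute to the sample size required to power the primary outcome". No share is given for them.

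**The concern.** Forty out of 400 is exactly 10%, the rate assumed for controls alone. If treatment cuts the hazard by 60%, the treated half of the trial must contribute far fewer events than the control half, so the overall proportion must lie well below 10%. The projection looks as if the control rate was applied to both arms.

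Two things are at stake. The first is feasibility: recruitment time, kit supply, budget and the timing of the monitoring board's reviews all follow from the enrolment figure. The second is power, but only if 400 is treated as the end of recruitment. Section 4.A can be read that way, and nothing in the plan says what happens if 400 pairs give fewer than 40 events.

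**Working it through.** **Inputs.** Control proportion 10%, hazard ratio 0.40, two-sided 5%, 80% power, 2% interim inflation, 5% multiple births, 400 pairs and 40 events (9.A; sidedness from 9.C). Balanced allocation (4.C.6), taken as 200 pairs per arm. Looks at 20, 30 and 40 events with critical values 2.74, 2.36 and 2.03 in absolute value (9.B). Multiples are taken as twins, so 400 pairs give 400 × 1.05 = 420 neonates.

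**1. The event target reproduces.** Schoenfeld's formula gives 4 × (1.96 + 0.8416)² / (ln 0.4)² = 37.4. With 2% inflation this is 38.1, the plan's 38. For multiples, 38 × 1.05 = 39.9, the plan's 40.

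**2. The inputs are read as intended.** Section 9.A also claims roughly 80% power for a 7-point risk difference with 400 pairs. For 10% against 3% with 200 per arm, the two-proportion power is 0.81. This supports reading 10% as the control-arm proportion and 400 as the total.

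**3. Expected events from 400 pairs.** Under proportional hazards the treated risk is 1 − 0.90^0.4 = 0.0413.
- One neonate per pair: 200 × (0.10 + 0.0413) = 20.0 + 8.3 = 28.3 events.
- With 5% twins: 210 × 0.1413 = 29.7 events.
- Treating 0.40 as a risk ratio (treated risk 4.0%): 28.0 and 29.4.

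The shortfall against 40 is about 25 to 30%.

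**4. What would give 40 from 400.** A 10% risk in both arms does (400 × 0.10 = 40), but that is a hazard ratio of 1. Keeping 0.40, solving 200 × [p + 1 − (1 − p)^0.4] = 40 gives a control risk of 14.1%, or 13.4% with 210 per arm. Reading 400 as the number per arm gives about 56 events.

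**5. Enrolment needed.** The average risk is (0.10 + 0.0413)/2 = 0.0706.

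| Events | Evaluable neonates | Pairs, 5% twins |
|---|---|---|
| 20 | 283 | 270 |
| 30 | 425 | 404 |
| 40 | 566 | 539 |

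Thus 400 pairs is about where the second interim look falls. Forty events need 539/400 = 1.35 times the stated pairs, or 566/400 = 1.42 times with one neonate per pair. Baseline-positive neonates come on top. The plan gives no share, so 0 to 10% is an assumption: 539 to 539/0.90 = 599 pairs with twins, or 566 to 629 without.

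**6. Power.** Using Φ(0.9163 × √d / 2 − z), where d is the number of events:
- 40 events, single look (z = 1.96): 0.826. Simulating the three looks with the stated boundaries (1,000,000 runs) gives 0.816.
- 28.3 events: 0.683 (z = 1.96) or 0.658 (z = 2.03).
- 29.7 events: 0.704 or 0.680.

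**7. Chance of reaching the later looks with 400 pairs.** Summing two independent binomials with 200 (210) per arm, the probability of at least 30 events is 0.39 (0.50), and of at least 40 events 0.017 (0.034).

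**The case against.** The strongest reply is that the trial is event-driven. Section 9.A says events drive power and that assignment continues until 40 are confirmed, the looks in 9.B are triggered by events, and no cap appears anywhere. The figure of 400 is worded as an anticipation in 9.A and as approximate in 4.A. On that reading the test, the error rate and the planned power are untouched, and the power loss describes a course the plan does not adopt. This stands. It confines the error to the enrolment projection and makes the 66 to 70% figure conditional. It does not make the projection right, and it does not explain why 4.A omits the event rule.

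A second objection is that twins are counted as extra neonates while their events are treated as independent. If the plan's 5% clustering inflation is respected, 40 events are worth 40/1.05 = 38.1. Power is then 0.807 for a single look or 0.797 with the stated boundaries, and near 400 pairs it is about 0.66 to 0.68. That is a fair refinement of about two points; the conclusion does not change.

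Third, 540 pairs is the favourable end of the range, since it counts twins as extra neonates and assumes no baseline-positive exclusions. This is also fair, and about 540 to 570 before exclusions is the better statement.

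Finally, the sentence in 9.A records what was expected before the trial began. That dates the projection, but the sentence still presents 400 as following from the 10% rate and the hazard ratio of 0.40, and it does not.

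**Conclusion.** The concern holds. The 400-pair projection is wrong as written: at the plan's own assumptions it yields about 28 to 30 events, and no reading that keeps both the 10% control rate and the hazard ratio of 0.40 produces 40. Forty events need about 540 to 570 pairs before baseline exclusions, at least 35% more than stated.

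Under the 40-event rule, power stays at about 80 to 83%, depending on whether the interim boundaries and clustering are counted. Only if recruitment ended near 400 would power fall to about 66 to 70%, with the 40-event analysis very unlikely to be reached.

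These figures assume 1:1 allocation, 10% as cumulative control risk, proportional hazards and no dropout. The point should be fixed, but it does not undermine the design.

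**What to change.** - In 9.A, state that 40 events are expected to need about 540 pairs with 5% twins (about 566 evaluable neonates), plus an explicit allowance for baseline-positive neonates. The 400 may stay as a record of the pre-trial expectation if the text says that it does not follow from the stated assumptions.
- Make 4.A agree, and say in both sections that the 40-event rule governs and that 400 is not a cap.
- If recruitment must end near 400, disclose about 28 to 30 expected events and about 66 to 70% power for a hazard ratio of 0.40, and restate the 40-event final look in 9.B.
- Separate and minor: 9.A gives power "for the secondary analysis of the indicator of concordant colonization within 90 days after randomization", while the risk-difference analyses in 9.C are set "by 4 and 8 weeks after randomization comparing the Treatment to Control group". Align the two.

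The cost is wording in 9.A and 4.A and a less favourable enrolment figure. The event target, primary test and boundaries stay as they are; only the fallback of ending near 400 would change the design.

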**Table 3. Power estimates based on anticipated outcomes**

Assumption about outcomes among twins	Time to concordant colonization		Power to detect a difference if concordant colonization rate in treated group is 2%
	HR detectable with 90% power	HR detectable with 80% power	
Independent (38 outcomes)	0.35	0.40	0.89
Dependent, 5% twins (40 outcomes)	0.35	0.40	0.87
Dependent, 10% twins (42 outcomes)	0.34	0.39	0.85

## B. Interim Analyses

Several interim analyses will be performed. We will perform interim analyses for efficacy based on the number of accumulated primary outcomes. Specifically, we will perform an interim analysis after 20 and 30 neonates have been identified to have the primary outcome of concordant colonization. After accruing 20 neonates with the primary outcome, the standard Cox proportional hazards model with main effect of treatment will be fit to estimate the treatment effect, i.e. the hazard ratio comparing the hazard of concordant colonization comparing the intervention and control groups, and the test statistic for the treatment effect will be computed using the methods described in Section

9.C. The DSMB will review the results of the Cox proportional hazards model to determine if the trial will stop for efficacy. The **minimum** criteria for stopping for efficacy will be if the test statistic for the hazard ratio is less than  $Z_r = -2.74$ . If the trial continues, after accruing 30 neonates with the primary outcome, the Cox proportional hazards model will be fitted. The DSMB will review the results of these statistical analyses to determine if the trial will stop for efficacy. The **minimum** criteria for stopping for efficacy will be if the test statistic for the hazard ratio is less than  $Z_r = -2.36$ . If the trial continues, after accruing the 40 neonates with the primary outcome, the treatment effect will be deemed statistically significant if the test statistic for the primary analysis as described below falls within the rejection region defined by  $Z_r = -2.03$ .

To define the above rejection regions, we applied an approximation to the error spending function of O'Brien and Fleming ( $f(t) = \min\{at^3, \alpha\}$ ) such that we spend the overall Type I error rate of 0.05 as 0.0062, 0.0148 and 0.029 after accruing 20, 30 and 40 patients, respectively. The derived rejection regions at each interim analysis (i.e.  $Z_r$ ) are based on the hazard ratio (equivalent to the log-rank test comparing the survival experience in the treatment groups) using an approximation to the information available at each interim analysis (i.e. number of accumulated events at the interim analysis divided by 4).

In addition to the interim analyses conducted to determine whether the trial should stop early for efficacy, the DSMB may request additional analyses to be performed to determine whether the trial should stop for futility after accruing 20 and 30 concordant colonizations.

### **C. Statistical analysis plan**

Final analysis methods and changes in the analyses from those described in the protocol will be documented in the Statistical Analysis Plan prior to locking the database and unmasking the assignment. A CONSORT flow diagram will be created. In addition, descriptive statistics will be calculated to describe the feasibility of the study including number of parent-neonate units approached by a study team member, proportion of parents that consent, proportion of parents colonized among consented, proportion of parents colonized who subsequently do not complete the treatment, and the distribution of adherence, as defined below, to the randomized treatment.

Analyses will be conducted according to the modified intention to treat (mITT) principal. The same day parents are randomized, the neonate will undergo baseline testing to determine baseline *S. aureus* colonization status. Neonates who test positive for *S. aureus* colonization at the time of randomization do not satisfy the inclusion criteria and will not be included in the analysis; hence defining the modified intention to treat analysis. Exploratory analyses of baseline characteristics for the treatment groups will be evaluated by Student t test for continuous data and Pearson's  $\chi^2$  test or Fisher Exact test for categorical data. No missing data should occur for baseline parent and neonate variables. No missing primary or secondary outcomes are expected. However, it is possible that neonates have no subsequent cultures between the baseline culture and NICU discharge, e.g. a neonate enters the study on Friday and is discharged on Sunday prior to their scheduled surveillance culture (Friday in this example) or discharge culture. Based on our definition of observation time (see Sections 5.A and 5.B), such neonates

will contribute no observation time for the analysis of the primary and secondary outcomes. A sensitivity analyses will be conducted where the observation time for these neonates will be defined as the time from randomization to NICU discharge. All tests will be 2-sided with a type-1 error rate set at 0.05. Data will be managed and analyzed using Stata, version 13.0 (Stata Corp., College Station, TX) and R: A language and environment for statistical computing (R Foundation for Statistical Computing, Vienna, Austria, 2014).

The primary analysis will evaluate our hypothesis that detection and treatment of *S. aureus* colonized parents with intranasal mupirocin and topical chlorhexidine gluconate bathing (Treatment Group) will decrease the risk of a child acquiring *S. aureus* with a concordant strain in the NICU within 90 days of randomization relative to the control parents (Control Group). The parent-neonate pair will be the unit of measure. For neonates that do not acquire concordant colonization within 90 days of randomization, their survival time will be computed as the time from randomization to the date of final culture (surveillance or discharge) within 90 days of randomization. We will define the treatment effect as the relative hazard of concordant colonization comparing the Treatment to Control group and will estimate this hazard ratio using the standard Cox proportional hazards model that includes only a main term for treatment. To account for the possibility of clustering within multiple gestation parent/neonate dyads, standard error estimates and bias-corrected and accelerated (BCa) confidence intervals for the log-hazard ratio will be derived using a bootstrap procedure. To preserve the correlation structure within the dyads, the bootstrap procedure will generate 10,000 bootstrap samples by sampling with replacement the parent/neonate dyads, as opposed to resampling the neonates. The analysis described above will be conducted at each pre-planned interim analysis with the test statistic derived from the estimated log hazard ratio from the Cox model and corresponding bootstrap standard error estimate, and the confidence level for the BCa bootstrap confidence intervals will be determined by the rejection region definitions specified in the Interim Analyses section (see Section 9.B).

Planned analysis of secondary outcomes will include the following: a) Repeat the primary analysis where time to concordant colonization will not be censored at 90 days after randomization; time will be defined as the time from randomization to the first of concordant colonization or last available culture (clinical, surveillance or NICU discharge), b) Define the treatment effect as the difference in the proportion of neonates acquiring concordant *S. aureus* by 4 and 8 weeks after randomization comparing the Treatment to Control group; this treatment effect will be estimated by taking the difference in the observed proportions comparing the Treatment and Control groups with standard error estimates and confidence intervals derived from the bootstrap procedure described above, c) Using the methods described above, estimate the treatment effect on the acquisition of *S. aureus* (regardless of concordant status), treated as both time to acquisition and the binary indicator for any acquisition by 4 and 8 weeks, and d) Using the methods described above, estimate the treatment effect on neonatal *S. aureus* infection, treated as both time to infection and the binary indicator for infection by 4 and 8 weeks. For the analysis of the *S. aureus* infection, we will first consider only *S. aureus* infections that occur prior to a neonate being identified as acquiring *S. aureus* colonization. For example, if a neonate acquires *S. aureus* colonization and then has a subsequent infection 7 days later, this infection will not be included. Only clinical cultures that occur before or on the same day as the first positive surveillance culture will be

considered. The NICU has a policy to decolonize all *S. aureus* colonized neonates which will impact the risk of infection in those that are first identified as colonized. Despite the possible independent impact of neonate decolonization on *S. aureus* infection risk, we recognize the importance of reporting all *S. aureus* infections in study patients; therefore, we will repeat the analysis, including *S. aureus* infections that occur at any time during a neonate's admission in the NICU. Lastly, a descriptive analysis of neonate mortality and bloodstream infections will be conducted, estimating the rate of occurrence separately for each treatment group.

Adverse events, as defined in Section 8, will be reported overall and separately by treatment group. Comparisons across treatment groups will be made using Fisher's Exact tests.

In addition, a series of planned secondary analyses will be conducted including subgroup analyses for the primary outcome, baseline-covariate adjusted analyses for the primary and secondary outcomes, per-protocol (PP) analyses for the primary and secondary outcomes and evaluation of patterns of loss and reacquisition of *S. aureus* among the parents (both treated and control).

Planned subgroup analyses include repeating the analysis for the primary outcome within strata defined by i) neonates with MRSA vs. those with MSSA, ii) collection site of colonization for the parent/caregivers, categorized as nares alone (i.e. all cultured parent/caregivers colonized in the nares) vs. nares + other (i.e. at least one parent/caregiver colonized in the nares) vs. non-nares; iii) LGA (large for gestational age) vs. SGA (small for gestational age); and iv) birthweight (< 1500g vs.  $\geq 1500$ g). The subgroup analyses will be based on Cox proportional hazards models that include a main term for treatment, a main term for subgroup (binary indicator) and the interaction between treatment and subgroup. Confidence intervals and the hypothesis test for no interaction will be derived based on the bootstrap procedure defined above.

We will explore the prognostic power of three pre-specified baseline covariates collected at the time of NICU admission which, if found to be prognostic, could be used in subsequent trials to improve the precision of the estimated treatment effect (Rubin et al 2008). Specifically, we will derive baseline-covariate adjusted estimates of the treatment effects defined for the primary and secondary outcomes. The baseline covariates include birth weight (treated as a continuous variable), an indicator for whether the neonate was born at the Johns Hopkins Hospital or the Johns Hopkins Bayview Medical Center (inborn) or admitted to the NICU from home or an outside hospital (outborn). For the survival outcomes, we will utilize the method developed by Lu and Tsiatis (2008) implemented in the R package "speff2trial". The method produces an estimate of the relative hazard of concordant colonization comparing the Treatment to Control group analogous to the hazard ratio parameter obtained from fitting a Cox proportional hazards model with a treatment indicator as the only covariate. In addition, the test for this relative hazard equates to applying the log-rank test in the case of proportional hazards. The method relies on constructing models for the treatment indicator and censoring indicator that account for chance imbalance in the selected baseline covariates. We will include all of the selected baseline covariates in the analysis as main effects. The large sample property of this estimator guarantees that if any of the selected baseline covariates are correlated with the outcome, the method yields an estimate of the relative

hazard that has statistical variance that is smaller or equal to the results of the Cox model. The estimate of the treatment effect will be constructed using the neonate as the unit of analysis. Similar to the methods proposed for the primary and secondary analyses, standard errors and confidence intervals for the covariate-adjusted estimate of the treatment effect will be based on a bootstrap approach to preserve the correlation structure within multiple gestation dyads. For the binary outcomes, e.g. acquiring *S. aureus* by 4 weeks after randomization, we will utilize novel methods proposed by Rotnitzky et al in 2012 and described in further detail in Colantuoni and Rosenblum (2014) that account for the specified baseline covariates. Similar to the methods proposed by Lu and Tsiatis (2008), the goal is to leverage information in the baseline covariates to produce an estimate of the treatment effect (i.e. absolute risk difference) that is as precise as or more precise than the unadjusted estimator of the treatment effect. We will follow exactly the algorithm detailed in Colantuoni and Rosenblum (2014) where the model for the treatment indicator we will be a logistic model with main effects of the specified baseline covariates.

We will conduct a per protocol (PP) analysis. Compliance to treatment will be defined first for the individual parent and then for the family or parent/neonate dyad (Table 4). Individual parents will be classified as: confirmed compliant where the parent returns a treatment kit with ointment tubes with a broken seal; reported compliant where the parent gave responses to questions about feasibility and potential adverse effects (see Section 4.B compliance monitoring); and non-compliant where a) kits were returned unused, b) the parent reported non-use, or c) parent was lost to follow up without reporting use. We will define *compliance to treatment* for the individual parent as confirmed compliant, with a sensitivity analysis including reported compliant in the definition of *compliance to treatment*. Family compliance will be defined as both parents satisfying the *compliance to treatment* definition, with a sensitivity analysis where we include partially compliant families, i.e. if the parent identified to be colonized with *S. aureus* is compliant based on the individual parent definition and the non-colonized parent is non-compliant. Baseline characteristics of the parents, including age, race, education level, and recent antibiotic use, will be compared across the individual parent compliance definitions, overall and separately by treatment group. Baseline characteristics of the ITT and PP neonates will be compared, overall and separately for each treatment group. The analysis of the primary and secondary outcomes described above will be repeated among the subset of parent/neonate dyads who are observed to be compliant. Note, that we will assume that all placebo group patients are compliant. We will conduct the PP subset analysis using this assumption and then separately incorporating the compliance definitions above to the placebo group as well. Conditioning on compliance, a post-randomization variable, may introduce bias into any treatment comparisons. Therefore, we will also implement a causal inference approach using available baseline parent and neonate variables within an inverse probability weighted approach to estimate the treatment effect for the primary and secondary outcomes, where the treatment effect compares what would have happened if all patients receiving the treatment were compliant vs. if all patients receiving the placebo were compliant.

